10.1 PRIMARY EFFICACY PARAMETER

The primary efficacy parameter will be the change from baseline in average BSFS score over 4 weeks of treatment period. The participant-reported BSFS is a 1 to 7 scale where 1 corresponds to a hard stool and 7 corresponds to watery stool. For each participant, all available (non-missing) postbaseline BSFS score of the treatment period will be used to calculate the average BSFS score.

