Participants enrolled in the treatment period will return to the study site for study visits at Week 2, Week 4 (end-of-treatment study visit), and for a post-treatment follow-up study visit at Week 6. Telephone contacts may be made to participants in lieu of an on-site visit at Week 2. A complete schedule of activities (SoA) is provided in Section 2. Participants who discontinue from the study before the Week 4 visit should return to the study site to complete the early termination assessments as soon as possible after stopping the study drug.

During the open-label treatment period, participants will record via the eDiary their daily IBS-D symptoms including stool consistency (BSFS), worst abdominal pain, abdominal bloating, bowel movement frequency, rescue medication usage, number of episodes of urgency in a day, and number of episodes of fecal incontinence, if any.

The actual eDiary data entered by the participants will not be provided to the investigative site staff at any time during the study to prevent any potential bias in subsequent participant entries. However, periodic notifications will be generated to inform the investigator of participants' ongoing compliance with eDiary entries and to alert investigators if participants have experienced episodes of constipation or have required excessive loperamide rescue medication for acute treatment of uncontrolled diarrhea.

The total duration of the study is up to 11 weeks, which includes: screening period (0-2 weeks), pretreatment period (2-3 weeks), 4-week open-label treatment period, and 2-week post-treatment follow-up period. A total of 6 study visits are planned for each participant:

- Screening, Week -3 to -5 (Visit 1) prior to Baseline visit
- Pretreatment, Week -3 to -2 (Visit 2) prior to Baseline visit
- Day 1 (Visit 3; first administration of study drug)
- Week 2 (Visit 4; Week 2 of treatment), may be done by telephone
- Week 4 (Visit 5; end of treatment/early termination)
- Week 6 (Visit 6; post-treatment follow-up)

The study design is presented in [Table 5-1](#).

Table 5-1 Study Design

Period	Screening ^a	Pretreatment ^a	Open-Label Treatment			Post-Treatment
Duration	0-2 weeks	2-3 weeks	4 weeks			2 weeks
Week	Screening	Pretreatment	Baseline	Week 2 ^b	Week 4 (EOT/ET)	Week 6 ^b (Follow-up)
Study Visit	1	2	3	4	5	6
Study Day			1	15 (± 2)	29 (± 2)	Visit 5 + 14 days (± 7)

7 α C4 = 7 α -hydroxy-4-cholesten-3-one; BA = bile acid

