7.7.3. Rescue Medicine

Loperamide hydrochloride may be used as rescue medication for acute treatment of diarrhea during the pretreatment and open-label treatment periods. Loperamide rescue medication use will be recorded by the participant in the eDiary.

[REDACTED]
Eluxadoline**7.8. Treatment after the End of the Study**

Not applicable.

8. Discontinuation/Withdrawal Criteria

Premature discontinuation of the study will occur when a participant ceases participation in the study, regardless of circumstances, before the completion of the study visits and procedures. Notification of early participant discontinuation from the study and the reason for study discontinuation will be sent to the sponsor and will be clearly documented on the eCRF.

Reasons for premature discontinuation from the study treatment and/or the study may include the following:

- Adverse event
- Death
- Lack of efficacy
- Lost to follow-up
- Non-compliance with study drug
- Other
- Physician decision
- Pregnancy
- Protocol deviation
- Site terminated by sponsor
- Withdrawal by subject

When a participant discontinues study treatment, the reason(s) for treatment discontinuation shall be recorded by the investigator on the relevant page of the eCRF. Whenever possible, all enrolled participants who prematurely discontinue study treatment will undergo all EOT/ET visit assessments.

It is vital to obtain follow-up data on any participant discontinuing study treatment because of an AE or SAE. In every case, efforts must be made to undertake protocol-specified safety follow-up procedures until resolution or stabilization.

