10.0 EFFICACY ANALYSES

The efficacy of eluxadoline will be based on eDiary measures related to improvements in IBS-D signs and symptoms. Participants will be required to access the eDiary each evening, preferably at the same time each day, to record daily IBS symptoms.

The efficacy analyses will be based on the mITT Population. Baseline for efficacy based on eDiary measures will be determined for the respective scores average over 14 days prior to the first dose of study treatment. Baseline for efficacy based on study visit measures (IBS-QoL and 7 α C4) will be the last assessment before the first dose of study treatment. Continuous variables will be summarized by number of participants and mean, SD, median, minimum, and maximum values. Categorical variables will be summarized by number and percentage of participants. All efficacy endpoints will be summarized by participant group (BAM or Non-BAM).

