16.2 DERIVED VARIABLES

During the open-label treatment period, participants will record via the eDiary their daily IBS-D symptoms. The average values of non-missing postbaseline will be derived for the following variables:

The primary endpoint: BSFS score;

The secondary endpoints: the worst abdominal pain score, the worst abdominal bloating score, the number of bowel movements and the number of urgent bowel movements.

Only non-missing postbaseline values will be used to calculate the average values. Imputation will not be applied to missing records. The denominator should be adjusted accordingly when average values are calculated.

The IBS-QOL is composed of 34 items scored on a 1-5 scale, where lower item scores indicate greater quality of life. All items are reversed prior to derivation of composite scores; thus, higher IBS-QOL total scores indicate greater quality of life. The transformation formula used for the IBS-QOL total score is

$$\text{Score} = 100 \times \frac{\text{sum of all items} - \text{lowest possible derived score}}{\text{possible sum range}}$$

Items	Lowest/Highest Possible Derived Score	Possible Sum Range
IBS-QOL total score	All items 34, 170	136

If 7 or more items are missing, the total score will be set to missing; otherwise, the total score will be calculated using the mean score of the non-missing items to replace the missing item.

All items reversed prior to derivation of overall and subscale scores: reversed score = 6 – original score.

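### Does the SAP need a table of loperamide rescue days by cohort to make the BAM versus non-BAM comparison of stool consistency readable?

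*SAP*

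**What the plan says.** Protocol 7.7.3 permits rescue on both sides of the first dose: "Loperamide hydrochloride may be used as rescue medication for acute treatment of diarrhea during the pretreatment and open-label treatment periods". It also fixes the record: "Loperamide rescue medication use will be recorded by the participant in the eDiary". Inclusion criteria 5.01 and 5.02 require at least 10 completed diary days in the 14 before Day 1 and rescue on no more than 3 of those 14 days.

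The SAP averages every available day in both periods. For baseline (10.0): "Baseline for efficacy based on eDiary measures will be determined for the respective scores average over 14 days prior to the first dose". For treatment (10.1): "all available (non-missing) postbaseline BSFS score of the treatment period will be used to calculate the average BSFS score". Section 16.2 repeats the rule: "Only non-missing postbaseline values will be used to calculate the average values". The secondary variables averaged there are "the worst abdominal pain score, the worst abdominal bloating score, the number of bowel movements and the number of urgent bowel movements". Rescue use is not among them, and the visible SAP does not mention loperamide.

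Two other places bear on the point. SAP 8.0 plans a listing of prior and concomitant medications by participant group, with drug names, from the eCRF. SAP 4.0 says that the specifications of tables, figures and listings are held in a separate document.

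**The concern.** The primary objective compares two non-randomised cohorts in an open-label study, and the comparison is read from descriptive summaries alone. Loperamide is given for diarrhea, so it acts on the outcome being measured. If rescue use changes from baseline to treatment differently in the two cohorts, part of the difference in BSFS change belongs to loperamide and not to eluxadoline. Bowel-movement frequency and urgent bowel movements are exposed in the same way.

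The protocol carries two expectations, and each is vulnerable. Section 3.1 expects greater efficacy without BAM; if BAM participants respond less and take more rescue as a result, the difference shrinks. Section 4 expects similar effects; an excess of rescue in one cohort would then make that cohort look better.

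Protocol 5.1 names seven daily eDiary items. Six of them feed a primary or secondary endpoint; rescue use is the one that does not, which looks like an oversight.

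**Working it through.** **What the documents provide.** The only design figure is the sample size, 12 + 12 = 24, which SAP 14.0 says is not statistically based. There is no planned power, SD or rescue rate to reproduce, so the check has two parts.

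**1. Is rescue invisible in the planned outputs?** Not entirely.

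- Protocol 7.7 records as prior medication everything taken in the 30 days before treatment, including over-the-counter drugs. That window covers the 14-day baseline. Everything taken after treatment starts is concomitant therapy.
- The minimum record is drug name and dates of administration (7.7). Section 7.7.2 adds indication, dose and frequency.
- SAP 8.0 lists these by participant group. With 24 participants, such a listing can be read by cohort and by period.
- The listing comes from the eCRF, whereas daily rescue is entered in the eDiary, and "The actual eDiary data entered by the participants will not be provided to the investigative site staff at any time during the study". The two records need not agree.
- Absence from SAP 16.2 is weak evidence of an omission. That section covers variables averaged for endpoints. It also omits the daily incontinence count, which 10.2 handles as a proportion. Rescue is not an endpoint in either document.

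What is missing from the visible SAP is therefore a count of eDiary rescue days by cohort and period.

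**2. How large could the effect be?** Let d be the fall in BSFS on a rescue day, and p_B and p_T the shares of baseline and treatment days with rescue. Then

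observed change = change without rescue − d × (p_T − p_B).

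The shift in the cohort comparison is d times the between-cohort difference in (p_T − p_B). The assumptions are d = 0.5 to 2 points and a full 28-day diary.

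From the entry criteria, the largest baseline share is 3/14 = 0.214, or 3/10 = 0.300 if only 10 diary days are completed.

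| Difference between cohorts | Share | d = 0.5 | d = 1 | d = 2 |
|---|---|---|---|---|
| 1 excess day in 28 | 0.036 | 0.018 | 0.036 | 0.071 |
| 3 excess days in 28 | 0.107 | 0.05 | 0.11 | 0.21 |
| 6 excess days in 28 | 0.214 | 0.11 | 0.21 | 0.43 |
| One cohort falls from 3/14 to 3/28, other unchanged | 0.107 | 0.05 | 0.11 | 0.21 |

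Use at a constant rate (3/14, then 6/28) cancels exactly, because both periods are averaged in the same way.

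For scale, the standard error of the cohort difference is SD × √(2/12). An assumed SD of 0.8 gives 0.327 and 1.2 gives 0.490. With t(22) = 2.074, the 95% half-widths are 0.68 and 1.02.

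- At d = 1, 3 excess days are 0.107/0.490 = 0.22 to 0.107/0.327 = 0.33 standard errors.
- At d = 1, 6 excess days are 0.214/0.490 = 0.44 to 0.214/0.327 = 0.66 standard errors.
- At d = 2, 6 excess days are 0.429/0.490 = 0.88 to 0.429/0.327 = 1.31 standard errors, still inside the narrower half-width of 0.68.

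An excess of 6 days in 28 is demanding. The share, 6/28 = 0.214, equals the entry ceiling of 3/14. If baseline use is the same in both cohorts, one cohort would have to average that ceiling rate throughout treatment while the other averaged none.

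**The case for a change.** The strongest case for a change is that the data exist, the table is cheap, and a reader of a non-randomised, untested comparison depends on descriptive context. The safeguards in Protocol 5.1 and 8.1 do not supply that context. Notifications serve "to alert investigators if participants have experienced episodes of constipation or have required excessive loperamide rescue medication", and excessive use may lead to stopping treatment, but both act on extreme individual use and would not reveal a moderate imbalance between cohorts. The medication listing is not a count of days and may differ from the diary.

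All of that stands as an argument for useful context. It does not show a defect. The table would display use and could not say how much of the BSFS difference is due to rescue. Rescue is taken because stools are loose, so it is partly a consequence of the outcome. Dropping or replacing rescue days would therefore bring in assumptions of its own, and each BSFS entry covers the past 24 hours, so a dose taken after the evening entry affects the next day's score. Nobody need alter the all-days average, and every primary and secondary result would be the same with or without the table.

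Nor can absence be confirmed. The table specifications were not available, Protocol 7.7.3 is partly redacted, and the text of SAP 16.8 on medication dates is not visible.

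**Conclusion.** No change to the plan is needed. The all-days average describes what happened to stool consistency under eluxadoline with rescue as permitted. It treats baseline, treatment and both cohorts alike, so only a differential change in rescue use can move the comparison. That movement is 0.05 to 0.21 points for 3 excess days in 28 and 0.11 to 0.43 for 6, against a standard error of 0.33 to 0.49. Only the upper end, with a 2-point fall per rescue day and a 6-day excess, is around one standard error. The per-day effect, the excess and the SD are all assumed; the documents give none of them.

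What remains is a reporting detail. Analysts can count eDiary rescue days by cohort when they describe this 24-person pilot, and the separate specifications may already provide for it. The conclusion would be different if the plan treated rescue days differently in the two periods or cohorts, or if rescue use were not recorded. Neither is the case.

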3.3. Benefit/Risk Assessment

Eluxadoline 100 mg twice daily (BID) demonstrated significantly greater composite responder rates as compared with placebo over 12 weeks and 26 weeks of treatment. Eluxadoline 75 mg BID demonstrated significantly greater responder rates than placebo over 12 weeks in both studies, and greater responder rates than placebo over 26 weeks of treatment in study IBS 3002, but not in study IBS 3001 ([Lembo 2016](#), [VIBERZI PI 2017](#)). The treatment effect of eluxadoline over placebo was observed within the first week and was maintained throughout the 26-week assessment period.

Other abdominal symptoms and measures of bowel function were also significantly improved with eluxadoline treatment as compared with placebo. Longitudinal analyses demonstrated that daily abdominal discomfort scores were significantly lower than placebo for both the 75 mg and 100 mg eluxadoline groups through Week 26. Daily bloating scores were significantly lower than placebo with eluxadoline 100 mg after Week 12 (Weeks 16, 20, 24, and 26). Risks for frequency of bowel movements and urgency episodes were also significantly lower than placebo for both eluxadoline doses through Week 26 of treatment. Additionally, both doses of eluxadoline were significantly superior to placebo with respect to the endpoints of adequate relief of IBS symptoms, scores for global symptoms, and scores on the IBS-Quality of Life questionnaire. Eluxadoline was significantly superior to placebo in all subpopulations explored ([Lembo 2016](#)).

In clinical studies, eluxadoline had a favorable tolerability profile with low rates of predominantly GI AEs. The most commonly reported AEs were constipation, nausea, and abdominal pain. Approximately 50% of constipation events occurred within the first 2 weeks of treatment, with most cases being of mild to moderate intensity.

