8.1. Discontinuation of Study Treatment

Participants must prematurely discontinue study treatment for reasons of safety including:

- an SAE considered by the investigator or the sponsor to be possibly related or related to investigational product,
- an AE of special interest (SO spasm, pancreatitis, severe constipation) see Section 9.2.8.1,
- pregnancy, see Section 9.2.7,

- signs of drug-induced liver injury (DILI), see Appendix 6, Section 12.6.

Participants may prematurely discontinue study treatment for reasons of safety including:

- the presence of intentional overdose or intentional misuse per investigator discretion,
- an AE indicative of a central nervous system (CNS) opioid effect, eg, pinpoint pupils, loss of consciousness, delirium, sedation or somnolence, euphoric, anxious or depressed mood, that in the opinion of the investigator or the sponsor is possibly related or related to the investigational product,
- a vital sign, and/or laboratory abnormality judged to be clinically significant by the investigator and that in the opinion of the investigator or the sponsor is possibly related or related to the investigational product,
- an intolerable AE (defined as an AE that subjectively would cause a participant to consider study withdrawal),
- an absence of bowel movements for ≥ 3 consecutive days, see Section 9.2.8.1, based on responses recorded via eDiary.
- the use of an excessive amount of loperamide rescue medication see Section 7.7.3.
- the occurrence of any other AE that in the opinion of the investigator or the sponsor is possibly related or related to the study treatment that represents a clinically significant safety risk to the participant.

See the schedule of activities (Section 2) for data to be collected at the time of treatment discontinuation and follow-up and for any further evaluations that need to be completed.

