9.1.1. Daily IBS Symptoms

Participants will record the following IBS-D signs and symptoms during their daily eDiary entry during the pretreatment period and throughout the 4 weeks of the open-label treatment period:

- Stool Consistency: Participants will be asked to use the BSFS to rate their stool consistency most representative of the past 24 hours. The participant-reported BSFS is a 1 to 7 scale where 1 corresponds to a hard stool and 7 corresponds to watery stool (Appendix 11, Section 12.11; O'Donnell 1988):
 - 1=Separate hard lumps like nuts (difficult to pass)
 - 2=Sausage shaped but lumpy
 - 3=Like a sausage but with cracks on surface
 - 4=Like a sausage or snake, smooth and soft
 - 5=Soft blobs with clear-cut edges (passed easily)
 - 6=Fluffy pieces with ragged edges, a mushy stool
 - 7=Watery, no solid pieces (entirely liquid)
- Worst Abdominal Pain: Participants will be asked to rate their worst abdominal pain in the past 24 hours. The participant-reported worst abdominal pain in the past 24 hours will be recorded on a 0 to 10 scale, where 0 corresponds to no pain and 10 corresponds to worst imaginable pain.
- Abdominal Bloating: Participants will be asked to rate their abdominal bloating in the past 24 hours. The participant-reported worst abdominal bloating in the past 24 hours will be recorded on a 0 to 10 scale, where 0 corresponds to no bloating and 10 corresponds to worst imaginable bloating.
- Frequency, Urgency and Incontinence: Participants will be asked to record the number of bowel movements, number of urgent bowel movements, and number of episodes of fecal incontinence, over the past 24 hours.

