6.3 MODIFIED INTENT-TO-TREAT POPULATION

All participants in Enrolled Population with ≥ 1 postbaseline assessment for Bristol Stool Form Scale (BSFS).

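### The available-day BSFS average can credit a participant who stops early for severe constipation with a large four-week improvement

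*SAP*

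**What the plan says.** SAP 10.1 sets the endpoint: "The primary efficacy parameter will be the change from baseline in average BSFS score over 4 weeks of treatment period". Stool form is rated on a "1 to 7 scale where 1 corresponds to a hard stool and 7 corresponds to watery stool", so any move towards hard stool is a further decrease. The same section states that "all available (non-missing) postbaseline BSFS score of the treatment period will be used to calculate the average BSFS score". SAP 16.2 adds that missing entries are not imputed and that the denominator is the number of recorded days. The analysis set, in SAP 6.3, is "All participants in Enrolled Population with ≥ 1 postbaseline assessment for Bristol Stool Form Scale (BSFS"), so a single entry is enough.

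Protocol 8.1 lists among the mandatory reasons to stop treatment "an AE of special interest (SO spasm, pancreatitis, severe constipation"). Section 9.2.8.1 repeats this for severe constipation, and Sections 8.1.1 and 8.1.2 rule out temporary stops and rechallenge, so the stop is permanent. On timing, Protocol 3.3 reports: "Approximately 50% of constipation events occurred within the first 2 weeks of treatment". It adds that most cases were mild to moderate.

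After a stop, Protocol Section 8 says that, whenever possible, "all enrolled participants who prematurely discontinue study treatment will undergo all EOT/ET visit assessments". Section 5.1 asks participants who leave the study early to attend as soon as they can after stopping. Section 9.1.1 describes diary entries "during the pretreatment period and throughout the 4 weeks of the open-label treatment period". No readable text says whether entries continue after an early stop, or would be counted if they did. Protocol 8.1 refers the reader to the schedule of activities for data collected at discontinuation, but that schedule is not readable in either document.

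**The concern.** The event that ends the record, too much effect on stool, is tied to the outcome being averaged. Averaging the remaining days is therefore not neutral. A participant whose treatment ended in the first week because of severe constipation carries the same weight in the cohort mean as one with 28 days of entries. If hard stools make up much of that short record, the participant counts as a strong responder over four weeks. Any later return of loose stools is not recorded unless diary entries continue.

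The primary objective compares participants with and without BAM, using descriptive means with 12 planned per cohort. If such stops were more frequent in one cohort, that cohort could appear to respond better partly because more of its members could not stay on the drug. Discontinuation reasons (SAP 7.0), treatment duration (SAP 9.1) and adverse events by severity (SAP 11.1) are reported by cohort, so an imbalance in stops would be visible. But no visible planned output shows how much of the primary result depends on it, because neither stop status nor number of diary days is set beside the endpoint.

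**Working it through.** The plan has no figure to reproduce. It gives no expected BSFS change, SD or stopping rate, and the sample size (12 + 12 = 24) is stated not to rest on statistical considerations. The check applies the SAP scoring rule to assumed diaries.

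**Inputs from the documents:** scoring rule (SAP 10.1, 16.2); 12 per cohort (Protocol 10.1, SAP 14.0); four weeks = 28 diary days.

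**Assumptions:** baseline BSFS 6.0; the diary patterns below; immediate return to baseline off drug.

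**Formulas:** let d be the number of recorded days and F the sum over those days of (6.0 − score).
- Change as scored by the SAP: −F/d
- Change over 28 days, with off-drug days at baseline: −F/28
- Shift in a 12-person mean: (F/d − F/28)/12

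| Diary before the stop | d | F | SAP change | 28-day change | Shift |
|---|---|---|---|---|---|
| 14 days at 4.5, then 3 at 1.5 | 17 | 21 + 13.5 = 34.5 | −2.03 | −1.23 | 0.797/12 = 0.07 |
| 7 days at 4.5, then 3 at 1.5 | 10 | 10.5 + 13.5 = 24 | −2.40 | −0.86 | 1.543/12 = 0.13 |
| 2 days at 5, then 3 at 1.5 | 5 | 2 + 13.5 = 15.5 | −3.10 | −0.55 | 2.546/12 = 0.21 |
| 3 days at 1.5 | 3 | 13.5 | −4.50 | −0.48 | 4.018/12 = 0.33 |

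**Lower baseline.** Inclusion criterion 2.06 admits a mean of 5.0. Each F then falls by d, to 17.5, 14, 10.5 and 10.5. The shifts become (1.029 − 0.625)/12 = 0.03, (1.40 − 0.50)/12 = 0.08, (2.10 − 0.375)/12 = 0.14 and (3.50 − 0.375)/12 = 0.26.

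**Days without stool.** The readable text gives no BSFS value for such a day. Suppose three unscored days follow the hard-stool days and drop out of both averages, so that 28 becomes 25. The first three shifts (baseline 6.0) are then (2.03 − 1.38)/12 = 0.05, (2.40 − 0.96)/12 = 0.12 and (3.10 − 0.62)/12 = 0.21. If the diary is 4 days at 5 followed only by unscored days, the SAP change is −1.00 and the constipation itself never enters the average.

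**Would the stopper be the largest improver of 12?** With 11 completers drawn from a Normal distribution with assumed mean −1.5 and SD 1.0, the probability is (1 − Φ((c + 1.5)/1.0))^11, where c is the stopper's change. This gives 0.93 at c = −4, 0.47 at −3 and 0.02 at −2.

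**The case against.** The strongest reply is that the direction and size are less certain than they first look. The SAP averages every recorded day, so normal or loose days before the constipation count as well. Severe constipation is defined in Protocol 9.2.8.1 by discomfort and limitation, not by BSFS, and the alert is three days without a recorded bowel movement, which may leave no score at all. Protocol 3.3 describes low rates of mainly gastrointestinal events. About half of constipation events therefore came after week 2, where dilution is strong. Only severe constipation forces a stop; three days without a bowel movement is an optional reason. All of this stands, and it is why the size is given as a range.

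A second reply is that existing outputs would expose the problem: reasons for stopping, exposure and adverse events by cohort, and the minimum and maximum of the endpoint itself. This stands in part. A reader might infer that nothing planned would show unequal stops, and that would be wrong. What is missing from the visible text is the link to the endpoint. Table and listing specifications are in a separate document (SAP 4.0) that is not available here.

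Third, on-drug stool form is a legitimate measure for the hypothesis of similar pharmacodynamic effects in Protocol Section 4, and this is an unpowered descriptive pilot. That also stands. It is a reason to keep the planned average and put a second summary beside it.

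**Conclusion.** The plan lets a short record stand as a four-week average when the reason for its shortness is the drug's effect on stool. Under the stated assumptions, one such participant shifts a cohort mean by about 0.07 to 0.21 BSFS points for mixed diaries, and by up to 0.33 if every recorded day to a Day 3 stop is at 1.5. The shifts are smaller with a baseline of 5.0. They are differences between two ways of summarising the same participant, and they rest on assumed diaries.

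Two stronger readings are not supported. A reader might infer that these participants are scored only on hard-stool days and so enter as the largest improvements. The rule uses all recorded days, and a stopper at −2 would rarely be the largest of 12 (0.02 under the assumed completers). A reader might also double the extreme case, with two stoppers in one cohort and none in the other, and expect a false difference of 2 × 0.33, about 0.67. That requires 2 of 12 (17%) stopping in this way, and the documents give no rate.

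The absence of diary continuation is a statement about the readable text only. If the schedule of activities already requires entries after a stop, the protocol part of the fix falls away and the SAP part remains.

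**What to change.** 1. **Protocol 8.1 and 9.1.1**, unless the schedule of activities already says so: a participant who stops study drug without withdrawing consent continues daily eDiary entries to Day 29.
2. **SAP 10.1 and 16.2:** keep the planned summary and state that it uses on-treatment days. Add a supplementary summary using all diary entries to Day 29 regardless of drug. State how a day without stool enters the BSFS average.
3. **Listing:** for each participant, show the number of diary days contributing, the last dose day and the reason for stopping. If the two summaries disagree on the cohort difference, the report says so.

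The cost is small. The device and the daily entry already exist, and only early stoppers are affected. The downside is slightly more diary burden for them, and their off-drug entries will probably be incomplete. No planned analysis is replaced, and no stopping or dosing rule changes.
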